13.10 Patient reported outcomes

Below is given short description of patient reported outcomes. Please refer to the document **PAREMA1 Case Report Form content** for full details of collected information.

13.10.1 Adverse events and device deficiencies

Participants are instructed to report adverse events experienced during the course of the study. The events can be encountered in relation to a treatment session or any time thereafter. Safety reporting will create an alert and site will call the participant without undue delay (within 1 business day) to follow up on the report.

13.10.2 Migraine Headache Pain Scale

Participants will be asked to report their migraine-associated headache pain via electronic Patient Reported Outcome (ePRO) app using a four-point Likert Scale. Participants will be prompted for this symptom rating at the initial report of aura symptoms and at the time points one, two, twenty-four and forty-eight hours after the initiation of treatment.

13.10.3 Other Migraine Symptoms

Participants will be asked to report their migraine symptoms via ePRO using a four-point Likert Scale, including the nausea, phonophobia, photophobia and functional disability. Participants will be prompted for this symptom rating at the initial report of aura symptoms and at the time points one, two, twenty-four and forty-eight hours after the initiation of treatment

13.10.4 Delay until treatment initiation

At the 0 time point, the participant is prompted to estimate how long time went by from the beginning of aura symptoms until the beginning of treatment.

13.10.5 Aura duration and symptoms

At the time point when the participant reports that the aura has stopped, he/she is prompted to estimate the duration of the aura phase (minutes), as well as indicate the type of aura symptoms experienced.

13.10.6 Use of rescue medication

The participants will via ePRO be prompted to answer whether they have used rescue medication, at the time points two, twenty-four and forty-eight hours after the initiation of treatment.

13.10.7 Impact on life and work

At the 48-hour time point, participants will via ePRO be prompted to rate:

- Impact of the migraine attack on participant's work/school attendance and ability to do household chores, during the first 48 hours since the beginning of the attack (4-point Likert scale)
- Impact of the migraine attack on participant's social life and leisure time, during the first
 48 hours since the beginning of the attack (4-point Likert scale)

13.10.8 Patient satisfaction (Stage 1)

48 hours after each attack start, participants will be asked to rate their subjective satisfaction with the device treatment's effect (satisfaction measured on 5 point scale: 5 = Satisfied, 4 = Partially Satisfied, 3 = Neutral, 2 = Partially Unsatisfied, 1 = Unsatisfied)

13.10.9 Assessment of blinding

At Site Visit 2, patients will be asked whether they believed they received the active or placebo device during Stage 1. This data will be used to compute the Bang Blinding Index (Bang et al., 2004)

13.10.10 Long term patient satisfaction (Stage 2)

Once each month during Stage 2, participants will be prompted to report how many MA attacks they have had during the past month, how many of these they treated with the study device, as well as their overall subjective satisfaction with study device treatment overall during the last month (satisfaction measured on 5 point scale: 5 = Satisfied, 4 = Partially Satisfied, 3 = Neutral, 2 = Partially Unsatisfied, 1 = Unsatisfied). The question also has the option of answering that the participant did not have any attacks during the past month.

13.10.11 Long term migraine drug and neurostimulator use

Each month during Stage 2, participants will be asked how many times in the past month they have taken respectively a prescription acute migraine drug, an over-the-counter acute analgesic or a neurostimulation device, with the intention to treat migraine. They will also be asked about the type and dose.

13.10.12 Migraine-related hospitalizations

Each month during Stage 2, participants will be asked whether they have been hospitalized for migraine over the last month, and if yes, how many days in total.

14 Risks and Benefits

This section gives an overview of the risks and benefits of the study. For a more detailed risk analysis please refer to the Investigator's Brochure.

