8.5.4 Post-market data

The Rehaler device was CE approved (Class I) in 2018 and put on the market on a limited scale from October 2018 until April 2020, in Denmark, Sweden and Germany. During this period, data and feedback was collected from users in order to ensure safety as well as improve the device, instructions for use and other aspects of the treatment.

If the present clinical study is successful, we intend to CE certify the device according to the new EU regulations (MDR), followed by resuming marketing of the device.

As detailed in the Investigator's Brochure, out of a total of 1450 patients that bought a Rehaler Starter Kit from 2018 to 2020, only two serious incidents occurred, the first with a patient who had the indication for use but also had intracranial hypertension, and the second with a patient who did not have the indication for use and who had previously undergone stenting of an unruptured brain aneurysm. In both incidents, the adverse event reported was headache.

Subsequently, the list of contraindications was expanded in order to prevent the occurrence of such incidents again in the future. Specifically, the following contraindications were added to the labelling and IfU:

- Previous aneurysm and/or brain surgery, including stenting
- Intracranial hypertension

Neither of the incidents qualified as Serious Adverse Events as defined in the MDR regulation (article 2, paragraph 58), since they did not incur a risk of death or permanent impairment, or led to hospitalization or a need for an acute medical or surgical intervention.

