15.1 Definitions

Device Deficiency

Inadequacy of a medical device with respect to its identity, quality, durability, reliability, usability, safety or performance. Device deficiencies include malfunctions, use errors and inadequacy in the information supplied by the manufacturer, including labelling.

This definition includes device deficiencies related to the investigational medical device or the comparator.

Adverse Event (AE)

An AE is any untoward medical occurrence, unintended disease or injury, or untoward clinical signs (including abnormal laboratory findings) in subjects, users or other persons, whether or not related to the investigational medical device and whether anticipated or unanticipated.

Adverse Device Effect (ADE)

Any AE related to the use of the investigational medical device.

This definition includes adverse events resulting from insufficient or inadequate instructions for use, deployment, implantation, installation, or operation, or any malfunction of the investigational medical device.

This definition includes any event resulting from use error or from intentional misuse of the investigational medical device.

This includes "comparator" if the comparator is a medical device.

Serious Adverse Event (SAE)

An AE that led to any of the following:

- a) Death,
- b) Serious deterioration in the health of the subject, users or other persons as defined by one or more of the following:
 - 1) a life-threatening illness or injury, or
 - 2) a permanent impairment of a body structure or a body function including chronic diseases, or
 - 3) in-patient or prolonged hospitalization, or
 - 4) medical or surgical intervention to prevent life-threatening illness or injury, or permanent impairment to a body structure or a body function,
- c) Foetal distress, foetal death, a congenital abnormality, or birth defect including physical or mental impairment

Planned hospitalization for a pre-existing condition, or a procedure required by the CIP, without serious deterioration in health, is not considered a serious adverse event.

Serious adverse device effect (SADE)

Adverse device effect that has resulted in any of the consequences characteristic of a serious adverse event.

Unanticipated Serious Device Effect (USADE)

Serious adverse device effect which by its nature, incidence, severity or outcome has not been identified in the current risk assessment.

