15.3 Adverse event recording

The Investigator will monitor the occurrence of adverse events for each subject during the course of the clinical study. Adverse events (AEs) may be reported by the participant, identified by the PI or documented in the medical record. All AEs regardless of source, must be recorded in the EDC system. Throughout the study, participants must immediately report any adverse events and device deficiencies experienced through the ePRO, which will be recorded by investigators in the electronic Case Report Form (eCRF). The Investigator must provide information on symptoms, date and time of onset, duration, severity, seriousness rating, causality, actions taken, outcome and any other pertinent information. All AEs occurring while in study must be documented appropriately regardless of relationship. All AEs will be followed to adequate resolution. Any medical condition that is present

at the time of screening will be considered as baseline and not reported as an AE. However, if the study participant's condition deteriorates at any time during the study, it may be recorded as an AE.

Changes in the severity of an AE will be documented to allow an assessment of the duration of the event at each level of severity to be performed.

A hard copy of the electronic AE section will be available to allow the Investigator to report SAEs and device deficiencies in the event the EDC is not available. The AE report must then be sent to: [contact]

Detailed instruction on reporting and completion of the AE section will be provided to the sites as part of the Site Initiation Visit (SIV).

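### Section 15.3 lets a site leave an unplanned migraine admission out of the AE data although section 15.1 makes it an SAE, and no supplied text links the monthly Stage 2 hospitalisation question to AE reporting

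*Protocol*

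**What the plan says.** **Definitions (protocol 15.1).** An AE is any untoward medical occurrence, "whether or not related to the investigational medical device and whether anticipated or unanticipated". An AE becomes serious if it leads to, among other things, "in-patient or prolonged hospitalization". The exemption reads "Planned hospitalization for a pre-existing condition, or a procedure required by the CIP, without serious deterioration in health".

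**Recording (protocol 15.3).** All AEs must be entered in the EDC system, whatever their source or relationship. The same section says that a medical condition present at screening counts as baseline and is not reported as an AE. If that condition "deteriorates at any time during the study, it may be recorded as an AE".

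**Reporting (protocol 13.10.1 and 15.4).** "Safety reporting will create an alert", and the site then calls the participant within one business day. Serious events are reported within 24 hours of the investigator's awareness.

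**The Stage 2 item (protocol 13.10.12).** "Each month during Stage 2, participants will be asked whether they have been hospitalized for migraine over the last month", and for how many days. This is Stage 2 exploratory endpoint 5 (11.4.2). SAP 1.7.3 compares it with the Site Visit 1 baseline and gives it no safety analysis.

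**Safety endpoint (protocol 11.2 and 16.6).** Device- or treatment-related AEs, and related SAEs or SADEs, are tabulated.

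**The concern.** Two rules in section 15 point in different directions for the same event. Section 15.1 classes an unplanned admission for migraine as serious. Section 15.3 leaves it to the site whether worsening of a condition present at screening is an AE at all, and makes no exception for worsening that meets a seriousness criterion. Migraine with aura is an inclusion criterion, so the permissive rule reaches the whole population.

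What is at stake is whether SAE data are complete and consistent across sites. An admission that is never entered as an AE gets no causality rating. It may not reach the sponsor's Medical Advisor, who reviews clinical events in a study without a Data Monitoring Committee (15.5). It would also be missing from the annual (S)AE overviews to ethics committees (15.4). This matters most in Stage 2, where everyone uses the active device and headache is both a listed device effect (14.1.1) and part of the underlying disease, so an individual assessment of cause is needed.

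**Working it through.** **1. Is an unplanned migraine admission an SAE under 15.1?** The AE definition does not exclude expected or disease-related occurrences, and in-patient hospitalisation is a seriousness criterion. The exemption for a pre-existing condition is limited to planned admissions without serious deterioration. It would be unnecessary if admissions for pre-existing conditions were already outside the definition. The answer is yes.

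**2. Does 15.3 require it to be recorded?**

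| Text in 15.3 or 15.4 | Force | Applies to a migraine admission? |
|---|---|---|
| All AEs entered in the EDC | must | Only once it is treated as an AE |
| Condition present at screening | not reported as an AE | Yes, migraine is present in all participants |
| Deterioration of that condition | may | Yes, with no exception for serious deterioration |
| Serious event reported within 24 hours of awareness (15.4) | must | Only once it is considered serious |

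The mandatory duties begin after the step that 15.3 leaves open. The plan permits omission but does not direct it.

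**3. Does another route close the gap in Stage 2?**
- The monthly question captures the admission, but no supplied passage says that a yes opens an AE form, raises the 13.10.1 alert or prompts a site query.
- Participants must report AEs immediately (15.3), and the diary offers an option for problems or adverse events (13.6). Both depend on the participant reporting the admission separately from the monthly question.
- The end-of-Stage-2 call asks about non-reported AEs (13.6.1). The schedule of events shows no planned site contact between Site Visit 2 and that call, which may be about 12 months later.
- Even when the site learns of the admission, step 2 still applies.

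**4. Scale.** The documents give no expected admission or SAE rate and no number entering Stage 2, so there is no figure to reproduce. What follows is illustration under assumptions. The exact (Clopper–Pearson) 95% limits for *x* events in *N* are:
- *x* = 0: upper limit = 1 − 0.025^(1/N). For N = 150 this is 2.43%.
- *x* = 1: lower limit = 1 − 0.975^(1/N), which is 0.017% for N = 150. The upper limit solves P(X ≤ 1) = 0.025, which gives 3.66%.

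| N entering Stage 2 (assumed) | One event counted (upper limit) | Event omitted (upper limit) |
|---|---|---|
| 136 | 0.74% (4.03%) | 0% (2.68%) |
| 150 | 0.67% (3.66%) | 0% (2.43%) |
| 200 | 0.50% (2.75%) | 0% (1.83%) |
| 240 | 0.42% (2.30%) | 0% (1.53%) |

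Here 136 is the SAP Table 1 figure for 200 randomised less dropouts, 200 and 240 are the SAP minimum and cap, and 150 is a round value between them.

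The chance that at least one participant has such an admission is 1 − (1 − r)^N. With an assumed proportion r of 0.2% to 2% and N from 136 to 240, the expected number is 0.27 to 4.8 and the chance of at least one is 0.24 to 0.99.

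**The case against.** The best defence is that the monthly question is an addition. Nothing says that it replaces AE reporting. Participants have a standing duty to report, investigators must record AEs from any source including the medical record, and both Site Visit 2 and the end-of-Stage-2 call ask about unreported events. Section 15.1, by exempting only planned admissions, already implies that unplanned ones are serious. Section 13.10 describes itself as a short description and refers to the Case Report Form content for detail. That document, the Safety Management Plan and the site-initiation instructions were not supplied and may contain the link.

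Much of this stands. It shows that a careful site would report the admission, and that a missing form trigger cannot be proved from a summary section. It does not remove the permissive wording in 15.3, which conflicts with 15.1 whatever the forms contain.

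A reader might also infer three stronger points, which the documents do not support:
- *That a wait of up to a month for the questionnaire breaches the 24-hour rule.* That clock runs from the investigator's awareness, so the two intervals are not comparable.
- *That a serious device effect would most likely appear as a migraine admission.* Section 8.5.4 does say of the two serious post-market incidents, "In both incidents, the adverse event reported was headache". It also says that neither met the MDR definition of an SAE or led to hospitalisation. Both patients had conditions that are now excluded (12.1.2, nos. 3–5), and 14.1.1 gives headache the lowest listed probability (below 0.1%).
- *That every omitted admission lowers the primary safety endpoint.* That endpoint counts only related events.

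**Conclusion.** The point holds as an inconsistency between 15.1 and 15.3, with an unlinked collection route in Stage 2. A site that follows 15.3 as written can leave out an event that 15.1 counts as serious.

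The effect is on the completeness of SAE data and of the overviews sent to ethics committees, whatever the relatedness. It reaches the primary safety endpoint only for admissions that would be judged device- or treatment-related. Section 15.2.2 classes cases that cannot be assessed as possibly related, but an unrecorded event is never assessed. Stage 2 has no comparator, so what changes is an absolute incidence and not a contrast between arms.

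The numbers are small but so are the expected counts. With 150 assumed to enter Stage 2, one omission turns 0.7% (0.02–3.7%) into 0% (0–2.4%). That comparison concerns SAE incidence, and carries over to the safety endpoint only if the event would have been rated related. The conclusion about 15.3 rests on the text alone. The conclusion about the missing link is conditional on the unsupplied form content and Safety Management Plan. The sponsor should correct this, but it does not threaten the efficacy analysis.

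**What to change.** 1. **Section 15.3.** Reconcile with 15.1 by stating that deterioration of a baseline condition *must* be recorded as an AE when it meets a 15.1 seriousness criterion. Name unplanned hospitalisation for migraine as an example, and require a causality rating.
2. **Section 13.10.12.** Have a yes open the AE form and send the 13.10.1 alert, or cite the existing link if the Case Report Form content or Safety Management Plan already has one. Reconcile the monthly answers against the SAE data before database lock.
3. **Section 16.6.** State that those admissions rated device- or treatment-related are counted in the safety endpoint. No unconditional inclusion is needed.

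The exploratory endpoint can stay as it is. The cost is a few sentences in the protocol, one trigger in the ePRO form and one reconciliation listing. Design, sample size and efficacy analyses do not change. The reported SAE count may become slightly less favourable.

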14.1 Known Potential Risks

14.1.1 Risks related to the active device

By increasing CO_2 in the inspired air, the device induces an increase in bodily CO_2 as well as a fall in pH, which are the intended physiological effects. With the device, the inspired CO_2 fraction is between 1.5% and 2.5% leading to an increase in P_{aCO2} of approximately 4 - 12 mmHg. This range has been in the previous experimental tests been found to be well-tolerated, safe and effective (Fuglsang et al., 2018; Johansen, 2017; Johansen et al., 2013); in the clinical studies undertaken using the device (in different but functionally equivalent forms), no serious adverse events occurred.

After having used the active device for five minutes, participants *may* start to experience harmless side effects which according to a benefit-risk ratio are judged as acceptable, and which for the purpose of the clinical investigation are categorized as *'expected side effects'*.

The expected side effects are (cf. (Fuglsang et al., 2018)):

- Deeper and/or faster breathing (hyperpnea due to the increase in P_{aCO2})
- Feeling slightly warmer or colder than normal
- Increase in salivation
- Increase in perspiration

Additional device effects have in the clinical pre-market data and in the post market surveillance been reported in a small percentage of patients using the device, including:

- Dyspnea (probability less than 10%)

- Mild nausea (probability less than 10%)
- Dizziness (probability less than 10%)
- Mild claustrophobia (probability less than 5%)
- Anxiety (probability less than 5%)
- Headache (probability less than 0.1%)
- Any other symptoms causing moderate to severe discomfort

The side effects listed above should be counteracted by decreasing the CO₂ setting of the Rehaler, in practice by moving the regulator (see Figure 2) to a lower setting. Study participants will receive very clear instructions about how to recognize and counteract such effects should they occur: respectively during the Training Session and in the Informed Consent Form and Instructions for Use (see these documents).

Apart from CO_2 effects, the risk assessment must also address the issue of possible hypoxemia. Any partial rebreathing device without an external source of compressed oxygen gas will inevitably lead to a decrease in the inspired oxygen level. However, individuals conforming to the in/exclusion criteria (i.e. without pulmonary or cardiovascular disease or anaemia) have a significant extra-capacity for oxygen uptake, meaning that decreases in the inspired oxygen pressure from the normal sea level value of 21 kPa (dry basis) down to 16 kPa are unproblematic and do not lead to hypoxemia (West, 2008). This corresponds to the situation which arises when a person travels from sea level to a high altitude. Signs of oxygen inadequacies upon exertion typically do not manifest themselves below altitudes of approx. 2200 meters, where the oxygen partial pressure is 16 kPa. In the present case, where the device users will be sitting at rest while using the device, the potential for hypoxemia is even smaller. This is supported by the arterial blood data which showed a drop of C_{aO2} of less than 2%, as well as the pulse oximetry data showing that the $S_{pO2\%}$ range was the same (95%-100%) with the study device as at baseline (see section 8.5.1).

Use of the Rehaler is contraindicated for the following:

- Chronic pulmonary disease (e.g. Chronic Obstructive Pulmonary Disease (COPD) or pulmonary fibrosis)
- Severe cardiovascular disease (e.g. symptomatic coronary artery disease, prior myocardial infarction, congestive heart failure (CHF)
- Cerebrovascular disease (e.g. prior stroke or transient ischemic attack, symptomatic carotid artery disease, prior carotid endarterectomy or other vascular neck surgery)
- Anaemia
- Sickle Cell Disease
- Uncontrolled intracranial hyper/hypo-tension
- Past or present cerebral aneurysm
- Individuals with previous brain surgery, including stenting
- Use in airplanes or at altitude over 2000 meters (6600 feet) above sea level
- Pregnant or breastfeeding women
- Children under the age of 18

Rehaler has potential interactions when used in conjunction with the following pharmaceutical agents:

1. Anesthetic agents: interaction can give rise to cardiac dysrhythmias.

- 2. Neuromuscular blocking agents and hypotensive agents: the change in pH induced by Rehaler can influence uptake, distribution and action of drugs (including neuromuscular blocking agents, and hypotensive anesthetic agents).
- 3. Adrenaline: carbon dioxide increases the uptake rate of adrenergic substances such as adrenaline.

